The investigator must maintain adequate and accurate records to enable the conduct of the study to be fully documented and the study data to be subsequently verified. These documents should be classified into two different separate categories (1) Investigator's Study File, and (2) Subject clinical source documents. The Investigator's Study File will contain the protocol/amendments, data collection forms, Independent Ethics Committee/Institutional Review Board and governmental approval with correspondence, sample informed consent, device records, staff curriculum vitae and authorization forms and other appropriate documents/correspondence. All records defined in 21 CFR 812.140 will be kept on file.

Subject clinical source documents include subject hospital/clinic records, physician's and nurse's notes, appointment book, original lab reports, special assessment reports, signed informed consent forms, subject screening and enrollment logs.

The investigator must keep these two categories of documents on file for at least 2 years after the latest of the following: completion, discontinuation of the study, or the regulatory submission for which the study is being performed is no longer under review. After that period of time the documents may be destroyed, subject to local regulations.

Should the investigator wish to assign the study records to another party or move them to another location, Regenesis Biomedical, Inc. must be notified in advance.

If the investigator cannot guarantee this archiving requirement at the investigational site for any or all of the documents, special arrangements must be made between the investigator and Regenesis Biomedical, Inc. to store these in a sealed container(s) off-site so that they can be returned sealed to the investigator in case of a regulatory audit. Where source documents are required for the continued care of the subject, appropriate copies should be made for storing outside of the site.

A. Source Documents and Background Data

The investigator shall supply the sponsor on request with any required background data from the study documentation or clinic records. This is particularly important when data requires clarification. In case of special problems/and or governmental queries or requests for audit inspections, it is also necessary to have access to the complete study records, provided that subject confidentiality is protected.

All forms should be typed or filled out using indelible ink, and must be legible. Errors should be crossed out but not obliterated, the correction inserted, and the change initialed and dated by the investigator or his/her authorized delegate.

B. Audits and Inspections

The investigator should understand that source documents for this trial should be made available to appropriately qualified personnel from the Regenesis Biomedical, Inc. Quality Assurance Unit or its designees or to health authority inspectors after appropriate notification. The verification of the data must be by direct inspection of source documents and patient charts.

XII. MONITORING THE STUDY

It is understood that the responsible Regenesis Biomedical, Inc. monitor (or designee) will contact and visit the investigator regularly and will be allowed, upon request, to inspect the various records of the trial (source documents and other pertinent data) provided that subject confidentiality is maintained in accord with local requirements.

It will be the monitor's responsibility to inspect the patient charts at regular intervals throughout the study to verify the adherence to the protocol and the completeness, consistency and accuracy of the data. The monitor should have access to laboratory test reports and other subject records needed. The investigator (or his/her designee) agrees to cooperate with the monitor to ensure that any problems detected in the course of these monitoring visits are resolved.

XIII. CONFIDENTIALITY OF TRIAL DOCUMENTS AND SUBJECT RECORDS

The investigator must assure that subjects' anonymity will be maintained and that their identities are protected from unauthorized parties. On documents submitted to the sponsor, subjects should not be identified by their names, but by an identification code. The investigator should keep a

subject enrollment log showing codes, names and addresses. The investigator should maintain documents not for submission to Regenesis Biomedical, Inc., e.g., subjects' written consent forms, in strict confidence.

XIV. PUBLICATION OF DATA AND PROTECTION OF TRADE SECRETS

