Endpoints	For this proof of concept study, the primary endpoints will be changes in Vibration Perception Threshold and Quantitative Sensory Testing between baseline and end of treatment. Secondary endpoints will be changes in nerve conduction velocity (NCV) of the sural nerve and amplitude from baseline to end of treatment, changes in Skin Perfusion Pressure (SPP) from baseline to end of treatment, change in Pain Intensity using the 11-point Numeric Pain Rating Scale (NPRS) from baseline to end of treatment, change from baseline in Brief Pain Inventory (BPI) and Brief Fatigue Inventory (BFI), change from baseline in Patient Global Impression of Change (PGIC), change from baseline in Hospital Anxiety and Depression Scale (HADS), and changes from baseline in neuropathy and foot ulcer specific quality of life instrument (NeuroQoL).
	Safety will be assessed through review of Adverse Event (AE) reports and concomitant treatments and medications. All concomitant drug or non-drug treatments used during the study will be recorded. Safety outcomes will be assessed at the interim visits and the end of study visit.
Study Procedures	Following informed consent and assessment of eligibility, subjects will complete Section A-History of the Michigan Neuropathy Screening Instrument (MNSI) with Section B- Physical Assessment completed by the site. A measurement of the depth of the right foot will be measured from the most inferior aspect of the medial malleolus to the plantar aspect of the foot when residing on the treatment pad. The depth should not be more than 8cm for eligibility. A finger stick will be performed on the subject to obtain a baseline HbA1c value (A1C Now [®] test kit) and subjects will complete a Urine Drug Screen in office. Subjects will undergo the Ankle-Brachial Index (ABI), Venous Insufficiency Assessment, and Pain Phase evaluation (at least 10 subjects in each of the 2, 3, and 4 pain phases will be enrolled). For subjects of child bearing potential a urine pregnancy test will be obtained.

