	At the Enrollment Visit (can be combined with Screening), subjects will have a finger stick performed to collect a baseline glucose value. If the Screening Visit and Enrollment Visit are not combined, eligibility will be re-assessed to confirm no changes, concomitant medications and assessments of Adverse Events will be obtained. Subjects will provide their baseline pain score over the last 24 hours using the Numeric Pain Rating Scale (NPRS) and will also complete baseline health economic questions, questionnaires including the Brief Pain Inventory (BPI), Brief Fatigue Inventory (BFI), Hospital Anxiety and Depression Scale (HADS), and the NeuroOoL Ouestionnaire.

Vibration Perception Threshold (VPT), Quantitative Sensory Test (QST) and Nerve Conduction Velocity (NCV) will be performed. Skin Perfusion Pressure (SPP) will be performed to obtain a baseline value of the plantar and dorsal aspect of the right foot. Eligible subjects will receive 2 active treatment devices (1 device for each foot). Subjects will be instructed in the use of the devices and will self-treat both feet twice daily (morning and evening; $8am \pm 2$ hours and $8pm \pm 2$ hours) for 60 days in the home environment. Each treatment will be 30 minutes in duration, treating both feet simultaneously. Subjects will be provided with a study diary for capturing their daily pain scores based on a 11-point numerical pain rating scale (NPRS) and weekly Patient Global Impression of Change Score (PGIC). Subjects will document pain scores each day after the morning treatment as instructed by the site at the Enrollment Visit. Every week the PGIC will be collected in the diary and the subject will document their overall status since the beginning of treatment. Subjects will either provide consent or not for biopsies to be obtained. Subjects that consent to the biopsies will have two 3mm punch skin biopsies obtained, one biopsy at the distal leg (10cm above the lateral malleolus) and one biopsy at the distal thigh (10cm above the superior margin of patella). Biopsies will be taken from the right leg to represent small nerve fiber innervation emanating from the deep peroneal nerve. At least two subjects in each pain phase category (2, 3, and 4 Pain Phase) will be obtained.

The site will contact the subject via telephone on Day 3 to assess subject adherence to treatment, completion of the diary, and any safety concerns and/or changes in concomitant treatments/medications.

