pressure in the angiosome is made. SPP (mmHg) at reactive hyperemia is recorded. A second measure of SPP will be obtained on the plantar aspect of the right foot directly below the location where the SPP was performed on the dorsal aspect of the right foot. SPP will be conducted at the Enrollment Visit, Day 61, and end of study visit (Day 121). An increase in SPP would be considered clinically meaningful.

Pain Intensity (PI): a validated 11-point Numeric Pain Rating Scale (NPRS) with scores (0-10) collected as patient-reported outcomes on a paper diary, at Screening for eligibility, at the Enrollment Visit for a baseline value, and Days 61, 75 and 91 to assess response (1-point decrease from baseline in average pain score over the last 24 hours). On the diary, PI will be assessed after each morning ($8am \pm 2$ hours) treatment. Subjects will report their average pain score over the last 24 hours. Diaries will be distributed and collected from the subjects every 2 weeks to ensure compliance.

Brief Pain Inventory (BPI): is a 32-question long form questionnaire that assesses the severity of pain and its impact on specific daily functions. Cronbach's alpha reliability ranges from 0.77-0.91. The BPI long form will be administered at the Enrollment Visit, Day 30, 61, 91, and end of study visit (Day 121). The change from baseline will be captured and assessed.

Brief Fatigue Inventory (BFI): is a 4-question assessment that assesses the level of fatigue and the impact of the fatigue on daily function over the last 24 hours. A global fatigue score is collected by averaging all items on the BFI. Cronbach's alpha reliability ranges from 0.82-0.97. BFI is patient reported and collected at the Enrollment Visit, Days 30, 61, 91, and end of study visit (Day 121). The change from baseline will be captured and assessed.

Patient Global Impression of Change (PGIC): a 7-point validated categorical scale of overall change in status since initiation of treatment with the study device. PGIC allows subjects to integrate into one overall evaluation of the different aspects of their response to treatment, including pain reduction, improvement in functioning and side effects. PGIC will be collected every 7 days in the paper diary, immediately following the morning treatment. PGIC serves to anchor within-subject changes in pain over the course of treatment.

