In a single question, subjects will be asked to describe their overall status compared to the start of the study ("Since the start of the study, my overall status is:"), and to score it as either very much worse, much worse, minimally worse, no change, minimally improved, much improved or very much improved (Appendix C). "Much Improved" and "Very Much Improved" are considered clinically meaningful results.¹ PGIC will be collected in the paper diary every 7 days immediately following the morning treatment during the 120-day treatment period. PGIC serves to anchor within-subject changes in pain over the course of treatment.

Hospital Anxiety and Depression Scale (HADS): is a patient reported assessment that detects stats of depression and anxiety. The subscales within the assessment assess the severity of the emotional disorder connected to having diabetic peripheral neuropathy. Subjects will complete the assessment at the Enrollment Visit, Days 30, 61, 91, and end of study visit (Day 121).

NeuroQoL: is a validated measure that measures the effects of diabetic peripheral neuropathy and its complications on an individual's quality of life. The questionnaire will be completed by the subject at the Enrollment Visit and end of study visit (Day 121).

3. Exploratory Efficacy Assessment

Biopsy: To assess c-fiber nerve density when treatment with Provant is administered. Biopsies will be taken from subjects that consent to them being taken. At least 2 subjects per pain phase category will be consented. One biopsy will be obtained at the distal leg, 10cm above the lateral malleolus on the right leg. A second biopsy will be obtained at the distal thigh, 10cm above the superior margin of the patella on the right leg. Both biopsies will be taken at the Enrollment Visit. The biopsies will be shipped overnight to the central lab. At the Day 121 Visit, a second set of biopsies will be obtained to the right of the baseline biopsies on the same subjects that consented at enrollment and shipped overnight to the central lab. At the end of the study, the biopsies will be compared to assess nerve fiber density.

4. Additional Study Assessments

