than the measured value. Standard deviation values will be formatted to two more decimal places than the measured value. Minimum and maximum values will be presented with the same number of decimal places as the measured value. The number and percentage of responses will be presented in the form XX (XX.X%). Pairwise differences between the treatment groups will be calculated and 95% confidence intervals constructed.

While no formal hypothesis testing is planned, probability values may be generated to determine the magnitude of the difference between subject groups for an endpoint. All p-values that round to 0.0000 will be presented as '<0.0001' and p-values that round to 1.0000 will be presented as '>0.9999'. P-values <0.05 will be discussed as being statistically significant.

All summary tables will include the analysis population sample size (i.e., number of subjects). Study Day 1 is defined as the day the subject receives their initial exposure to the active study device. All *study days* are determined relative to the day of initial treatment with the study device. Baseline values will be defined as those values recorded closest to, but prior to, the first active study treatment during the initial phase of the study. Date variables will be formatted as DDMMMYYYY for presentation. Where appropriate, only the measurements from the right foot will be used in the calculations.

D. Adverse Events

All summaries of adverse events will be based on treatment-emergent adverse events. Adverse events will be provided in a listing. The number and percentage of subjects experiencing adverse events will be summarized. Summaries by maximum severity and relationship to the study device (active or sham) will also be provided. Serious adverse events and adverse events leading to discontinuation from the study will be presented. Treatment-related adverse events will be defined as adverse events with investigator assessment of related or possibly related. In summaries of adverse events by severity and relationship to study device, patients reporting multiple episodes will be counted once under the worst severity and the strongest relationship, respectively. Serious adverse events will also be presented by relationship to treatment. The number of patients with at least one adverse event will be tabulated for each treatment group. The number of adverse events for each treatment group will also be tabulated.

E. Sample Size

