APPENDIX C – SUBJECT DIARY FOR DAILY PAIN SCORE AND WEEKLY GLOBAL IMPRESSION OF CHANGE

PATIENT: _____ Week Start Date: _____

Treat Both Feet, Simultaneously, Twice Daily for 30 minutes, 8am +/- 2 hours and 8pm +/- 2hours.

Circle the Pain Score which represents your average Pain over the last 24 hours after completing your Morning (am) treatment.

On the scale below, a score of 0 represents No Pain whereas a score of 10 represents the Worst Possible Pain. Every 7 days, mark your overall status compared to the start of the study.

			0	l 2 Mild	3	4 5 Mode	6 rate	7 8	3 9 Severe	10		
		No Pain										Worst Possible Pain
Date:		0	1	2	3	4	5	6	7	8	9	10
Date:		0	1	2	3	4	5	6	7	8	9	10
Date:		0	1	2	3	4	5	6	7	8	9	10
Date:		0	1	2	3	4	5	6	7	8	9	10
Date:		0	1	2	3	4	5	6	7	8	9	10
Date:		0	1	2	3	4	5	6	7	8	9	10
Date:		0	1	2	3	4	5	6	7	8	9	10
	Since the start (check one bo	t of the	study,	my ove	rall sta	tus is:						
	Very Muc	h Wors	e	Muc	h Wor	se [Mini	mally V	Vorse	  1	lo Chai	nge
	🗌 Mi	nimall	y Impro	oved	🗌 Mu	ich Imp	roved		Very M	uch Imp	proved	

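### After randomisation the weekly PGIC still rates change since study start, and no planned analysis separates induction gain from change after the switch

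*Combined protocol and SAP*

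**What the plan says.** - **Question put to the subject.** Section III.L.2 says that "subjects will be asked to describe their overall status compared to the start of the study". The diary in Appendix C uses the same reference: "Every 7 days, mark your overall status compared to the start of the study". There is one diary form and no separate version for use after randomisation.
- **Duration.** III.L.2 also states: "PGIC will be collected in the paper diary every 7 days immediately following the morning treatment during the 120-day treatment period". Rating therefore continues through the randomised phase.
- **Other wordings.** The scale definition, in the synopsis and in III.L.2, refers to "overall change in status since initiation of treatment with the study device". The synopsis under Study Procedures says "the subject will document their overall status since the beginning of treatment".
- **Design.** All subjects start on active devices. Responders at Day 61, 75 or 91 hand these in and are randomised 1:1 to active or sham through Day 120 (III.K and VI.B).
- **Analysis.** VI.C tabulates change from baseline to Day 120, and separately to the last observation, in randomised subjects, with arm differences and 95% intervals. It sets the reference before induction: "Baseline values will be defined as those values recorded closest to, but prior to, the first active study treatment". It describes no PGIC analysis relative to randomisation.

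**The concern.** The randomised comparison asks what happens after responders move to new active or sham devices. The PGIC asks about the whole period since study start. A sham subject who loses half of the induction gain can truthfully still answer on the improved side, because the worse categories apply only below the pre-study state. III.L.2 treats the top two categories as clinically meaningful, so a subject who is deteriorating after the switch could still be counted there.

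The other repeated endpoints share the pre-induction baseline, but most are absolute scores (VPT, QST, NPRS, BPI, BFI, HADS), and change since randomisation can be derived from them directly. The PGIC is a recalled change whose reference is built into the question, with recall of up to about four months by Day 120. At stake is the sensitivity of one secondary endpoint to loss of benefit on sham, in a study of at most 40 subjects.

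**Working it through.** The documents give no SD, effect size or power for the PGIC, and the sample of 40 is one of convenience (VI.E). There is no figure of the plan to reproduce. The check has four steps.

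**1. Reference points.** First treatment is on Day 1, the morning after the Enrollment Visit (III.J). Start of study, read as Enrollment (Day 0), is 1 day earlier. Read as Screening, which is up to 14 days before Enrollment (IV.A), it is at most 14 + 1 = 15 days earlier. The wordings thus give about two time points, both before induction.

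**2. Ratings available.** Weekly rating over 120 days gives 120/7, so 17 entries. Entries before randomisation are the whole weeks in 60, 74 and 90 days.

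| Randomised | Before | After |
|---|---|---|
| Day 61 | 8 | 9 |
| Day 75 | 10 | 7 |
| Day 91 | 12 | 5 |

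Every randomised subject who keeps the diary has a PGIC rating from shortly before the switch.

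**3. Bias.** Write the study-start rating as S = G + L, where G is the induction gain and L the change after the switch. Randomisation comes after G has arisen, so G has the same expectation in both arms and the expected arm difference in S equals that in L. A simulation of 20,000 trials confirmed this (20 per arm; assumed SD of G and of L both 1; true difference 1; uncorrelated). The mean difference was 1.00 with either rating. The standard error was 0.45 for S and 0.32 for L, matching √(2 × 2/20) and √(2 × 1/20).

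**4. Precision (illustration; every input is assumed).** True loss on sham 0.8 category, SD of L 0.8, SD of G 0.5 to 1.5, 15 per arm, correlation ρ between G and L.

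SD(S) = √(s_G² + 0.8² + 2ρ × s_G × 0.8), and d = 0.8/SD(S). The chance that the 95% interval excludes zero comes from the two-sample noncentral t with 28 degrees of freedom.

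| Rating | ρ | s_G | SD | d | Chance |
|---|---|---|---|---|---|
| Since switch (L alone) | any | any | 0.80 | 1.00 | 0.75 |
| Since start | 0 | 0.5 | √0.89 = 0.94 | 0.85 | 0.61 |
| Since start | 0 | 1.0 | √1.64 = 1.28 | 0.62 | 0.38 |
| Since start | 0 | 1.5 | √2.89 = 1.70 | 0.47 | 0.24 |
| Since start | -0.5 | 0.5 | √0.49 = 0.70 | 1.14 | 0.86 |
| Since start | -0.5 | 1.0 | √0.84 = 0.92 | 0.87 | 0.64 |
| Since start | -0.5 | 1.5 | √1.69 = 1.30 | 0.62 | 0.37 |

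The study-start rating is the less precise of the two only when s_G > -2ρ × 0.8. At ρ = -0.5 that means s_G above 0.8.

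**Adjustment for the last pre-switch rating.** If that rating recorded G exactly, the residual SD would be 0.8 × √(1 - ρ²). That is 0.80 at ρ = 0 (d = 1.00, chance 0.75) and 0.69 at ρ = -0.5 (d = 1.15, chance 0.86), whatever the SD of G. Within this model the adjusted comparison is at least as sensitive as the unadjusted study-start rating in every row. A coarse 7-category rating measures G with error, so in practice it would recover part of this and not all.

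**The case against.** The strongest case for leaving the plan alone has four parts.

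- **Stated role.** The protocol says that the PGIC anchors within-subject pain change over the course of treatment, and pain change also runs from the pre-induction baseline. A since-start question fits that role. This stands, and it is why the item should be kept. It does not answer how the arms are to be compared.
- **Data already in hand.** Weekly ratings on both sides of the switch allow an adjusted analysis without a new question. This stands too, and it shapes the fix. But VI.C does not plan such an analysis. The detailed separate SAP that section VI mentions is not part of the text reviewed, so one there cannot be ruled out.
- **Fragile size.** All inputs are assumed, and the loss can reverse, as the 0.86 against 0.75 shows. If sham subjects lose half of their own gain (mean gain 1.6, residual SD 0.8, 15 per arm), simulation gives 0.66, 0.47 and 0.32 for the study-start rating against 0.73, 0.67 and 0.59 since the switch. The direction holds, but the gaps are mostly smaller.
- **Trial-wide baseline, no formal testing.** Correct, and it limits the importance of the point.

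A reader might go further in three ways that the documents do not support:

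- *The PGIC comparison is biased.* It is not, because randomisation follows induction.
- *The protocol uses three different reference points, and this causes the merging.* There are three wordings but about two time points, 1 to 15 days apart. Any of the wordings would merge the two periods.
- *The reference becomes unclear once new devices are issued.* Subjects answer only the diary stem, which is tied to study start, and VI.C ties treatment start to the induction phase.

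**Conclusion.** The point holds as a minor, inexpensive improvement. The post-randomisation PGIC combines induction gain with change after the switch, and the plan as written does not separate them. The arm difference remains unbiased. The likely cost is precision and sensitivity to loss of benefit on sham, with recall and a ceiling on the improved side as further, unquantified contributors.

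The size cannot be derived from the documents. Under the assumptions shown, the chance of an interval excluding zero falls from 0.75 to between 0.61 and 0.24 when gain and later change are uncorrelated. At a correlation of -0.5 the study-start range is 0.86 to 0.37. A loss is therefore likely if induction gains differ widely between subjects, and absent or reversed if they are similar and larger gains are followed by larger losses. The PGIC is a secondary endpoint in a proof-of-concept study without formal testing, so nothing central depends on it.

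**What to change.** **Main change, in VI.C.** Base the active-sham PGIC comparison on the post-randomisation rating (Day 120, and last observation), adjusted for the subject's last weekly PGIC before randomisation. A linear model on the 1 to 7 score with arm and that rating gives an adjusted difference with a 95% interval, in keeping with the rest of VI.C. State which diary entry counts as the last one before randomisation and what happens if it is missing. Cost: a few sentences and one table, with no new data.

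**Optional addition.** In diaries issued from the randomisation visit on, add one weekly 7-point line, *Since I received my current devices, my overall status is:*, and use it for the active-sham comparison. Cost: one more line for about 4 to 9 weeks (30 to 60 days), possible confusion of two similar lines on paper, and some risk of prompting guesses about allocation. Unlike the adjustment, it cannot be added after the data are collected.

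**Keep** the study-start item for change over the whole study.

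**Editorial.** Use one reference wording in the synopsis, III.L.2 and Appendix C. The synopsis also lists the endpoint as a change from baseline, although the PGIC is itself a change rating and none is made before treatment. Naming the Day 120 rating by arm would settle that.
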